## 9.2 SAMPLE SIZE DETERMINATION

**Sample Size Calculation for SCUT II Primary Analysis: BSCVA.** We power the study for each pairwise comparison. Specifically, we will be comparing (Specific Aim 1) CXL plus early steroids (arm 3) versus steroids and sham cross linking (arm 2), and (Specific Aim 2) early steroids with sham CXL (arm 2) versus standard therapy (arm 1). The power calculation was based on the primary outcome, 6-month BSCVA. We informed the calculation with measurements from the first Steroids for Corneal Ulcers Trial (SCUT), among patients enrolled with between 20/60 and 20/400 vision. The SCUT trial measured BSCVA at baseline, 3-months, and 12-months. We conservatively used the 12-month outcome measure for the calculations since there was no 6-month measurement. The standard deviation of BSCVA at 12 months was 0.293. Since the primary analysis will adjust for baseline BSCVA, we used an estimate of the residual standard deviation, which is  $SD_r = SD\sqrt{1 - r^2}$ , where  $r$  is the correlation between the baseline measure and primary endpoint. In SCUT, the correlation between baseline and 12-month BSCVA among patients with between 20/60 and 20/400 vision at enrollment was 0.216. We thus assumed a residual standard deviation of  $0.293\sqrt{1 - 0.216^2} = 0.286$ . Assuming a significance level of  $0.05/2=0.025$ , and allowing for approximately 15% loss to follow up, we estimate that we will have 80% power to detect a 1.4-line difference (logMAR 0.14) between groups with 93 study participants per arm (279 total). This calculation applies to each of the two prespecified primary outcomes for this trial (corresponding to the two separate research questions), and is based on the standard power formula for the T-test (using an estimated residual standard deviation). Note that if the trial were to enroll 60 patients per arm, the minimum detectable effect under all the same assumptions would be 1.8 lines (logMAR 0.18). See SCUT II SAP Section 1.5.6 for details on interim power analysis.

**SCUT II Sample Size Calculation for Secondary Outcome: Microbiological Cure.** Studies have suggested that in addition to providing an initial diagnosis, repeated culture can be used to assess response to treatment and is highly correlated with clinical outcomes such as visual acuity. We will re-culture all study participants 30 minutes after CXL or sham CXL (Day 2) to assess the effect of CXL on rate of microbiological cure. We hypothesize that those in the CXL group (Arm 3) will have a higher rate of microbiological cure on Day 2 cultures than those randomized to the Standard Therapy (Arm 1) or Early

Steroid Group (Arm 2). Participants in both arms 1 and 2 will serve as the comparison group increasing the power in this analysis.

For microbiological outcomes, we will be comparing sham cross-linking to actual cross-linking, with specimens collected just prior to any administration of antibiotics (as discussed in the Manual of Operations). This comparison will be conducted contrasting Arm 3 to Arms 1 and 2 combined (which undergo sham cross-linking). We expect that approximately 70% of patients will show positive baseline cultures; only culture positive patients are likely to contribute information to the microbiological outcome. Taking into account loss to follow-up, we anticipate 80% power to detect at least a 26% difference in absolute terms between those experiencing cross linking (Arm 3) and those who did not receive cross linking (Arm 1 and Arm 2). The calculation assumes a comparison of two proportions. This is a prespecified secondary outcome.

Note that for both of these prespecified secondary analyses, the final hypothesis test will be conducted at an alpha of 0.025 (thereby applying a Bonferroni correction for two hypothesis tests).

**SCUT II Effects Stratified by Presence of Drug resistant Organisms.** This analysis is similar to the microbiological outcome in the secondary analyses, in that we contrast culture-positive patients from Arm 3 to culture-positive patients from Groups 1 and 2 (Specific Aim 3). Prior studies suggest a drug resistance to moxifloxacin probability of between 0.34 and 0.43, depending on prior exposure to moxifloxacin. We hypothesize that when drug resistant organisms are present, outcomes will be more favorable when cross-linking is conducted. The outcome variable is visual acuity. We anticipate approximately 80% power to detect a difference of approximately 3 lines in outcomes, assuming 35% of individuals are drug resistant at baseline (based on simulation; details available upon request). The calculation assumed 15% loss to follow-up. This is a prespecified secondary analysis.

See [Section 9.4.1](#) for details regarding pre-specified analyses.

**REAGIR Primary outcome, BSCVA at 6 months.** The sample size calculation for REAGIR used the same assumptions as the SCUT II sample size calculation for BSCVA. Assuming a significance level of 0.05, allowing for approximately 15% loss to follow up, we estimate that we will have 90% power to detect a 1.1-line difference (logMAR 0.11) between groups with 165 study participants per arm (330 total). For the same sample size and under the same assumptions, the detectable difference at 80% power is 1.0-lines (logMAR 0.10). These calculations were based on the standard power formula for the T-test (using an estimated residual standard deviation).

**REAGIR II Primary outcome, BSCVA at 6 months.** The sample size calculation for REAGIR II uses the same assumptions as the SCUT II sample size calculation for BSCVA. Assuming a significance level of 0.05, allowing for approximately 15% loss to follow up, we estimate that we will have 80% power to detect a 5.3-lines difference (logMAR 0.53) between groups with 30 study participants per arm (60 total). For the same sample size and under the same assumptions, the detectable difference at 90% power is 6.1-lines (logMAR 0.61). These calculations were based on the standard power formula for the T-test (using an estimated residual standard deviation).

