## 9.4 STATISTICAL ANALYSES

### 9.4.1 ANALYSIS OF THE PRIMARY EFFICACY ENDPOINT

The **Statistical Analysis Plans** for SCUT II, REAGIR, and REAGIR II include more detail about planned analyses. The primary outcome will be 6-month BSCVA, and the primary analysis of each trial will use the same approach. We will use multiple linear regression models to evaluate BSCVA measured at 6 months with covariates for treatment arm (expressed as a binary indicator variable for steroids and a binary indicator variable for cross-linking), indicators for study site (randomization strata), and BSCVA measured on Day 1 (before treatment). We propose a two-sided alpha of 0.025 for each pairwise primary comparison. Specifically, we propose to contrast Groups 1 and 2 using a linear model in which we use baseline visual acuity and a binary indicator for assignment to Group 2 as predictors, and BSCVA as the outcome variable. We then propose to contrast Groups 2 and 3 separately using a model with baseline visual acuity and a binary indicator for assignment to Group 3 as predictors, with BSCVA as the outcome variable.

For study participants who experience perforation or the need for TPK this will be noted and BSCVA will be recorded prior to performing surgery (either corneal glue or TPK). The last observation (at 3 weeks or 3 months) will be carried forward (LOCF) as the 6-month BSCVA, but a separate secondary analysis will include these study participants actual 6-month visual acuity.

A supplementary analysis using linear mixed effects regression will be conducted to analyze all BSCVA data (including 3-week and 3-month observations). The model will include baseline BSCVA and treatment assignment as covariates (fixed effects) plus a random effect for patient to allow for repeated measures over time. Such analyses will be sharply distinguished from the primary pre-specified analysis. Permutation testing will be the basis of inference. Specifically, we will conduct 10,000 random permutations of treatment assignment, and conduct the primary regression analysis on these re-

randomized data sets. We will then compare the observed regression coefficients to the randomization distribution, reporting the quantiles.

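### SCUT II's fixed 0.025/0.025 split over its two primary contrasts is valid, but Holm's step-down would give a better chance of confirming both aims at the same sample size and 5% family-wise error

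*Protocol*

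**What the plan says.** Protocol 9.2 (SCUT II primary analysis) names two contrasts. Aim 1 is "CXL plus early steroids (arm 3) versus steroids and sham cross linking (arm 2") and Aim 2 is "early steroids with sham CXL (arm 2) versus standard therapy (arm 1"). The calculation is made "Assuming a significance level of $0.05/2=0.025$ , and allowing for approximately 15% loss to follow up", and it claims "80% power to detect a 1.4-line difference (logMAR 0.14) between groups with 93 study participants per arm (279 total"). Power is stated for each contrast separately, and no joint power is given.

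Protocol 9.4.1 makes the same level the analysis rule: "We propose a two-sided alpha of 0.025 for each pairwise primary comparison". Section 9.4.2 repeats 0.05/2 for scar size. For the secondary tests, 9.2 describes the 0.025 as "applying a Bonferroni correction for two hypothesis tests".

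Neither the protocol nor the supplied SAP contains a step-down, gatekeeping or alpha-recycling rule, and no reason is given for the fixed split. The supplied SAP covers REAGIR only. The SCUT II SAP, whose Section 1.5.6 the protocol cites for the interim analysis, is not among the documents.

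**The concern.** Each primary contrast faces a threshold of 0.025 whatever the other one shows. If the UVX contrast were overwhelming and the steroid contrast had p = 0.03, the plan would declare steroids not significant. Control of family-wise error at 5% does not require that: once one of two hypotheses has been rejected at 0.025, the other may be tested at 0.05 (Holm).

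The protocol treats the two aims as separate research questions and anticipates benefit on both. That is the situation in which a step-down helps. What is at stake is the chance of answering both questions positively with the patients already planned.

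**Working it through.** **Inputs, all from Protocol 9.2 unless noted.** "The standard deviation of BSCVA at 12 months was 0.293"; correlation with baseline 0.216; 93 per arm; about 15% loss; difference 0.14 logMAR; two-sided alpha 0.025 (also 9.4.1); 1:1:1 allocation (Synopsis). The interim analysis is ignored throughout.

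**Step 1: reproduce the plan's figure.**
- Residual SD: 0.293 × √(1 − 0.216²) = 0.286, as stated.
- Evaluable per arm: 93 × 0.85 ≈ 79.
- Standard error of a contrast: 0.286 × √(2/79) = 0.0455.
- Standardised effect: 0.14 / 0.0455 = 3.077.
- Power at 0.025 (critical value 2.241): Φ(3.077 − 2.241) = 79.8%; 79.1% with the noncentral t.
- The detectable difference at 80% power is 0.140.

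The stated 80% stands. Solving for n gives 80 evaluable, or 80/0.85 ≈ 95 enrolled per arm, close to 93.

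**Step 2: dependence.** Group 2 enters the two contrasts with opposite signs. The covariance is −σ²/n and each variance is 2σ²/n, so the correlation is −0.5.

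**Step 3: joint probabilities.** Let c₁ = 2.241 (0.025) and c₂ = 1.960 (0.05), with Z₁ and Z₂ bivariate normal, correlation −0.5.
- Bonferroni, both: P(Z₁>c₁, Z₂>c₁) = 60.5%.
- Holm, both: P(Z₁>c₁, Z₂>c₂) + P(Z₁>c₂, Z₂>c₁) − P(Z₁>c₁, Z₂>c₁) = 73.6%.
- Holm, per contrast: 79.8% + (73.6% − 60.5%)/2 ≈ 86.3%.

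Simulation with 4 million trials agrees. Each cell gives Bonferroni → Holm:

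| True effects (logMAR) | Power per contrast | Both positive | At least one positive |
|---|---|---|---|
| 0.14, 0.14 | 79.8% → 86.3% | 60.5% → 73.6% | 99.1%, unchanged |
| 0.14, 0.10 | 79.8% → 84.7%; 48.2% → 57.7% | 32.8% → 47.0% | 95.3%, unchanged |
| 0.10, 0.10 | 48.2% → 53.8% | 15.0% → 26.2% | 81.5%, unchanged |
| 0.14, 0 | real effect 79.8% → 80.0%; null 2.5% → 4.2% | not applicable | 80.7%, unchanged |

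**Step 4: error control.** Under the global null, the chance of any false rejection is 4.6% with either method. With one null contrast and a very large effect on the other (0.5), Holm rejects the null contrast 5.0% of the time and Bonferroni 2.5%. Holm stays within 5% in every case.

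**Sensitivity for both effects at 0.14.** With no loss to follow-up (93 per arm), the chance of both goes from 72.9% to 83.2%. With an assumed correlation of 0, it goes from 63.7% to 74.8%.

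**The case against.** The split is prespecified, valid and used consistently. The protocol's goal is power for each comparison, and that goal is met; the documents never adopt the chance of both aims succeeding as a design criterion. All of this stands, so this is an option for improvement.

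A reader might infer that the split is an error, or that SCUT II is underpowered. The documents do not support either reading, because the 80% reproduces.

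A reader might also infer that Holm is free. It is not. The fixed split holds a null contrast at 2.5%, whereas Holm lets that reach 4.2% when the other effect is 0.14, and up to 5% when it is larger. Someone who treats the aims as wholly separate questions may value the tighter limit.

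The gain also needs both effects to be real. For steroids that is uncertain on the protocol's own account: the first steroid trial found no overall effect (P=0.82, Section 2.2), and benefit appeared only in subgroup analyses.

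Intervals are less tidy too. The two 97.5% intervals have about 95.4% simultaneous coverage. Reading the stepped-down contrast with a 95% interval lowers joint coverage to about 93.1% when both effects are 0.14.

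Finally, timing matters. The Synopsis says SCUT II is closed to enrolment, and 4.1 plans an interim look at one third of the outcome data. The documents do not say whether results have been unmasked.

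**Conclusion.** The point holds as a low-cost improvement. At effects of 0.14 logMAR on both contrasts, Holm adds about 13 points to the chance of confirming both aims (about 60% to 74%) and about 6.5 points to power per contrast. To reach the same joint power, Bonferroni would need about 94 evaluable per arm, or 94/0.85 ≈ 111 enrolled: 18 more per arm, 54 in all, in a trial that has stopped enrolling.

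The figures rest on the protocol's SD and loss rate, equal arms, normal approximations and no interim look. Two limits belong with any statement of the gain: the chance of at least one positive contrast is the same under both methods, and with one real effect of 0.14 the added power for it is only 0.2 points.

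Extending the step-down to the secondary tests in 9.2 may look natural, but no gain has been worked out for them, so the point is confined to the two primary contrasts. Whether the SCUT II SAP already contains a step-down cannot be checked; the fixed rule in 9.4.1 makes it unlikely.

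**What to change.** Make the change only if SCUT II is still masked and its SAP has no step-down rule already. If the SAP has one, align 9.2 and 9.4.1 with it. If results have been unmasked, leave the split as it is.

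State in 9.2, 9.4.1 and the SCUT II SAP that, at the final analysis, the smaller of the two primary p-values is tested at two-sided 0.025 and, if it is rejected, the other is tested at 0.05. Replace each threshold by the final-look boundary of the same spending function at total alpha 0.025 or 0.05, so that alpha spent at the interim is accounted for. Record the date of the change and the masking status. Keep 80% for 0.14 logMAR as the minimum power per contrast.

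Keep the 97.5% intervals as the simultaneous ones, and label any 95% interval for the stepped-down contrast as marginal.

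The cost is a short amendment plus the boundary calculation, with no effect on sample size, data collection or patient management. Two downsides should be written down with it: rejection of a null contrast can rise from 2.5% to as much as 5% when the other effect is real, and a contrast declared significant at the second step may have a 97.5% interval that includes zero.

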### Objectives:

**Specific Aim 1: To determine if corneal cross-linking with riboflavin (UVX) is a beneficial adjuvant in the treatment of smear- and/or culture-positive bacterial ulcers.**

- a. We anticipate that UVX will result in better best spectacle corrected visual acuity (BSCVA) at 6 months compared with antibiotic alone.
- b. We anticipate that UVX will result in faster microbiological cure rates, smaller scar size and lower rate of corneal perforation compared with antibiotic alone.

**Specific Aim 2: To determine if early topical steroids are a beneficial adjuvant in the treatment of smear- and/or culture-positive bacterial ulcers.**

- a. We hypothesize that those randomized to early topical steroids will have improved BSCVA at 6 months compared with antibiotic alone.

**Specific Aim 3: To determine which ulcer characteristics predict the most benefit from the addition of adjuvant corneal cross-linking and/or early steroids.**

- a. We hypothesize that culture positive bacterial ulcers with drug resistant organisms, as measured by MIC50, will benefit more from adjuvant UVX than those with antibiotic susceptible organisms.

**Specific Aim 4: To determine if cross linking with rose bengal (RB-PDT) is a beneficial adjuvant in the treatment of fungal, acanthamoeba, and smear or culture negative corneal ulcers.**

- a. We hypothesize that there will be improved visual acuity at 6 months among those randomized to adjuvant RB-PDT after controlling for baseline visual acuity.
- b. We anticipate that there will be smaller infiltrate/scar size and decreased rate of perforation and/or need for TPK at 6 months among RB-PDT treated patients.

**Specific Aim 5: To determine if corneal cross-linking with rose bengal (RB-PDT) is a beneficial adjuvant in the treatment of smear- and/or culture-positive bacterial ulcers.**

- a. We hypothesize that study participants treated with topical antibiotics plus adjunctive RB-PDT will have better best spectacle corrected visual acuity at 6 months compared to those treated with antibiotics alone.

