### 3 OBJECTIVES AND ENDPOINTS

OBJECTIVES	ENDPOINTS	JUSTIFICATION FOR ENDPOINTS
Primary		
Specific Aim 1: To determine the effect of UVX on best spectacle-corrected visual acuity	Best spectacle-corrected visual acuity at 6 months	The most clinically important outcome for patients
Specific Aim 2: To determine the effect of early topical steroids on best spectacle-corrected visual acuity	Best spectacle-corrected visual acuity at 6 months	The most clinically important outcome for patients
Specific Aim 4: To determine the effect of RB-PDT on best spectacle-corrected visual acuity for acanthamoeba and fungal keratitis	Best spectacle-corrected visual acuity at 6 months	The most clinically important outcome for patients
Specific Aim 5: To determine the effect of RB-PDT on best spectacle-corrected visual acuity for bacterial keratitis	Best spectacle-corrected visual acuity at 6 months	The most clinically important outcome for patients
Secondary		
Specific Aim 1: To assess the effect of UVX on microbiological cure	Repeat culture at Day 2	Culture status is highly related to clinical outcomes. This will allow us to assess for development of drug resistance during treatment.
To assess the effect of early topical steroids on microbiological cure	Repeat culture at Day 2	Culture status is highly related to clinical outcomes and one concern with topical steroids is that it might prevent resolution of infection.
Specific Aim 4: To assess the effect of RB-PDT on microbiological cure	Repeat culture at Day 2	Culture status is highly related to clinical outcomes. This will allow us to assess for development of drug resistance during treatment.
Specific Aim 3: To assess the relationship between UVX and drug resistant organisms	Interaction of minimum inhibitory concentration (MIC) and UVX on best spectacle-corrected visual acuity	Drug resistance is a concern, and the Infectious Disease Society of America recommends looking for novel treatments for bacterial infections. UVX does not use antibiotics.
Specific Aim 4: To assess the relationship between RB-PDT and drug resistant organisms	Interaction of minimum inhibitory concentration (MIC) and RB-PDT on best spectacle-corrected visual acuity	Culture status is highly related to clinical outcomes. This will allow us to assess whether RB-PDT is more effective when organisms are resistant to topical antimicrobials

OBJECTIVES	ENDPOINTS	JUSTIFICATION FOR ENDPOINTS

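### The Aim 3 acuity contrast puts a no-steroid arm into the comparator: UVX effects by resistance stratum carry half the steroid effect, and the MIC-by-UVX interaction is biased if the steroid effect varies with MIC

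*Protocol*

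**What the plan says.** Protocol Section 9.2, in the paragraph on SCUT II effects by drug resistance, introduces the analysis as similar to the microbiological one: "we contrast culture-positive patients from Arm 3 to culture-positive patients from Groups 1 and 2 (Specific Aim 3". It then says "The outcome variable is visual acuity" and gives no time point. On size it says: "We anticipate approximately 80% power to detect a difference of approximately 3 lines in outcomes, assuming 35% of individuals are drug resistant at baseline".

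The pooling comes from the microbiological cure paragraph just before it: "This comparison will be conducted contrasting Arm 3 to Arms 1 and 2 combined (which undergo sham cross-linking". The reason given there is power: "Participants in both arms 1 and 2 will serve as the comparison group increasing the power in this analysis".

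The question asked is about UVX alone. Aim 3a in the Synopsis expects that ulcers with resistant organisms "will benefit more from adjuvant UVX than those with antibiotic susceptible organisms", and the endpoint in Section 3 is "Interaction of minimum inhibitory concentration (MIC) and UVX on best spectacle-corrected visual acuity".

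In Section 1.1, allocation is 1:1:1. Group 1 receives placebo and sham UVX, Group 2 difluprednate and sham UVX, and Group 3 difluprednate and UVX. For the primary UVX question (Aim 1), Sections 9.2 and 9.4.1 compare Arm 3 with Arm 2 only. Section 9.4.1 also describes "treatment arm (expressed as a binary indicator variable for steroids and a binary indicator variable for cross-linking" in the primary regression. Section 9.4.2 gives no MIC model for SCUT II, and the SAP supplied covers REAGIR.

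**The concern.** Pooling Arms 1 and 2 is reasonable for an outcome that steroid cannot yet have touched. Acuity at follow-up is not such an outcome, because by then Arms 2 and 3 have had steroid and Arm 1 has not. All of Arm 3 but only about half of the comparator is steroid-treated, so the contrast no longer isolates UVX.

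Aim 2 exists because steroid may change acuity. Section 3 also records a concern that steroid could hinder resolution of infection, and such an effect might well depend on whether the antibiotic works against the organism. In that case part of a steroid-by-resistance effect would be reported as UVX-by-resistance, or would mask it.

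**Working it through.** **Inputs**
- Protocol 9.2: 93 per arm, 15% loss, 70% culture-positive, 35% resistant, a 3-line difference (0.30 logMAR), and a steroid design effect of 0.14 logMAR.
- Residual SD 0.286: stated in 9.2 for the primary analysis, assumed here for Aim 3.
- Two-sided alpha 0.025: stated in 9.2 for the secondary tests. That it covers Aim 3 is a reading, so 0.05 is also shown.
- Arm 1 share of the pooled comparator: 93/186 = 1/2.
- Resistant v susceptible stands in for MIC, as in the plan's own power statement.

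**1. What the pooled contrast estimates.** Let s be the steroid effect and u the effect of UVX on top of steroid. Stratum means are m (Arm 1), m + s (Arm 2) and m + s + u (Arm 3).
- Within a stratum: (s + u) − s/2 = u + s/2. With s = 0.14 the excess is 0.07.
- Interaction (resistant minus susceptible): (u_R − u_S) + (s_R − s_S)/2. If s_R = s_S the excess is 0. If they differ by 0.14 it is 0.07; if by 0.20, 0.10.

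**2. Reproducing the stated 80%.** Evaluable per arm: 93 × 0.85 × 0.70 = 55.3. Cells: Arm 3 has 19.4 resistant and 36.0 susceptible; Arms 1+2 have 38.7 and 71.9.
- SE = 0.286 × √(1/19.4 + 1/36.0 + 1/38.7 + 1/71.9) = 0.286 × √0.1192 = 0.0987.
- Power = Φ(0.30/0.0987 − 2.241) = Φ(0.80) = 78.7%.
- Detectable difference at 80% power = (2.241 + 0.842) × 0.0987 = 0.304.

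This is close to the stated figures. At alpha 0.05 the results are 86.0% and 0.277.

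**3. Arm 3 v Arm 2 only.**
- SE = 0.286 × √(2 × (1/19.4 + 1/36.0)) = 0.286 × √0.1589 = 0.114, larger by √(2/1.5) = 1.155.
- Power at 0.30 = Φ(0.30/0.114 − 2.241) = Φ(0.39) = 65.2%.
- Detectable difference = 3.083 × 0.114 = 0.351, about 3.5 lines.

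At alpha 0.05 the results are 74.9% and 0.319. The stated 80% at 3 lines therefore depends on including Arm 1.

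**4. Simulation with no UVX effect** (55 per arm, 35% resistant, SD 0.286, 2,000 runs, nominal 2.5%). Negative means better acuity. Each entry is the mean estimate, with the rejection rate in brackets.

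| Steroid effect, susceptible / resistant | Pooled, resistant stratum | Pooled interaction | Pooled plus steroid main effect | Arm 3 v Arm 2 interaction |
|---|---|---|---|---|
| −0.14 / −0.14 | −0.069 (8.2%) | 0.001 (1.7%) | 0.001 (1.9%) | 0.001 (2.0%) |
| −0.14 / 0 | 0.000 (2.7%) | 0.070 (5.8%) | 0.070 (6.1%) | 0.003 (3.0%) |
| −0.10 / +0.10 | 0.049 (5.2%) | 0.099 (10.4%) | 0.099 (10.4%) | −0.001 (2.9%) |

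A steroid main effect alone leaves the false interaction in place. Adding a steroid-by-resistance term removes it, with the same precision as Arm 3 v Arm 2: for a true interaction of 0.30, simulated power is 63.4% and 63.2%, against 76.6% pooled.

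**The case against.** **The endpoint is an interaction.** A reader might infer that any steroid effect contaminates the MIC-by-UVX result. It does not: a steroid effect equal across MIC cancels, as the first simulation row shows. The main-effect question belongs to Aim 1, which already uses Arm 3 v Arm 2. This stands, and it limits the unconditional bias to the stratum-specific UVX estimates.

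**The size for the interaction is assumed.** A reader might infer a one-line bias. That needs steroid effects that differ by 0.20 between resistant and susceptible ulcers, and no figure in the documents supports this. Section 2.2 reports no overall steroid effect on 3-month acuity in SCUT (P=0.82), and Section 2.3.1 says SCUT gave no evidence that steroids potentiated infection. These overall results do not exclude variation with MIC, but they make a large crossover less persuasive.

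**The model may be adjusted elsewhere.** The paragraph sits in the sample-size section and points to Section 9.4.1, which has separate indicators and refers to a SCUT II SAP not supplied here. So the documents do not show that the final Aim 3 model is unadjusted. But nothing in them applies those indicators to Aim 3, and a steroid main effect alone would not be enough.

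**Pooling buys precision.** The pooled interaction has the lower mean squared error unless its bias exceeds √(0.114² − 0.0987²) ≈ 0.057, that is, unless the steroid effect differs by more than about 0.11 between strata. That is large beside a design effect of 0.14. This is a fair reason to keep the pooled result as a sensitivity analysis. It does not make it an estimate of the UVX interaction.

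**Day 2 culture.** A reader might infer that pooling there is beyond question. Section 6.1.1 starts steroid 24 hours after antibiotics, which follow the repeat culture. Sections 1.1 and 6.1.1 also start study drug within 24 hours of enrollment, and 6.1.1 allows UVX up to 48 hours after enrollment. On that second timing steroid could come before the culture.

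**Conclusion.** The concern holds in a limited form. As written in Section 9.2, the Aim 3 acuity contrast does not isolate UVX. Stratum-specific UVX effects carry half the steroid effect: 0.07 logMAR at the design value of 0.14. The MIC-by-UVX interaction carries half of any difference in steroid effect across MIC, and nothing if there is no such difference.

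The stated power is not an arithmetic error. It reproduces at 78.7% under the pooled contrast, given the SD and alpha assumed for Aim 3. For the contrast that answers Aim 3a it is about 65% at 3 lines.

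This is a secondary analysis, and the primary UVX comparison is not affected. The documents do not give the Aim 3 time point; 6 months would be an inference from the primary endpoint. What the SCUT II SAP says remains unknown.

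**What to change.** - For the Aim 3 acuity endpoint, estimate UVX-by-MIC from Arm 3 v Arm 2, or from all three arms with both steroid-by-MIC and cross-linking-by-MIC terms. Report the cross-linking-by-MIC term. The pooled contrast may stay as a sensitivity analysis.
- State the acuity time point.
- Restate the detectable difference as about 3.5 lines (about 65% power at 3 lines), with the SD, culture-positive share, loss and alpha it assumes.
- Align Section 9.2 with the SCUT II SAP, and record whether the change was made before unmasking.
- Reconcile the two statements of when study drug starts in Sections 1.1 and 6.1.1. Pooling for the Day 2 culture is justified only if steroid starts after that culture.

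The cost is wording and precision; no new data are needed. Section 1.1 describes SCUT II as closed to enrollment, so the lost power cannot be recovered by recruiting more patients.

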## 4 STUDY DESIGN

### 4.1 OVERALL DESIGN

The Steroids and Cross-linking for Ulcer Treatment (SCUT II) and Rose Bengal Electromagnetic Activation with Green light for Infection Reduction (REAGIR) trials are international, randomized, double-masked, sham and placebo controlled, clinical trials; and Rose Bengal Electromagnetic Activation with Green light for Infection Reduction II (REAGIR II) is a randomized, double-masked feasibility study. The purpose of these studies is to determine differences in 6-month visual acuity between medical antimicrobial treatments alone versus antimicrobial treatment plus corneal cross-linking (CXL), as well as to further evaluate findings from subgroup analyses of SCUT.

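### REAGIR II's stated detectable differences (0.53 and 0.61 logMAR) do not follow from the SCUT II assumptions they are said to use, which give about 0.23 and 0.26–0.27

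*Protocol*

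**What the plan says.** Protocol 9.2 gives one paragraph to the REAGIR II sample size. It opens: "The sample size calculation for REAGIR II uses the same assumptions as the SCUT II sample size calculation for BSCVA". It then takes a significance level of 0.05 and about 15% loss to follow-up, and reports "80% power to detect a 5.3-lines difference (logMAR 0.53) between groups with 30 study participants per arm (60 total"). For the same sample size, "the detectable difference at 90% power is 6.1-lines (logMAR 0.61"). The stated method is the usual t-test power formula with a residual SD.

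The borrowed assumptions appear earlier in 9.2, under SCUT II: "The standard deviation of BSCVA at 12 months was 0.293", and "the correlation between baseline and 12-month BSCVA among patients with between 20/60 and 20/400 vision at enrollment was 0.216". From these the protocol derives a residual SD of 0.286. The supplied documents give no other SD for REAGIR II.

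Two other statements in 9.2 use the same SD. For SCUT II, at the stricter alpha of 0.025, if the trial were to "enroll 60 patients per arm, the minimum detectable effect under all the same assumptions would be 1.8 lines (logMAR 0.18"). For REAGIR, at alpha 0.05 with 165 per arm, "the detectable difference at 80% power is 1.0-lines (logMAR 0.10"), and 0.11 at 90% power.

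Protocol 4.1 says that REAGIR II "is a randomized, double-masked feasibility study".

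**The concern.** A detectable difference above five lines is out of proportion to its neighbours. SCUT II with 60 per arm is said to detect 0.18 logMAR. Halving the arm size should raise that by a factor of about 1.4, not to 0.53, and the less strict alpha in REAGIR II should bring it down again.

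Six-month BSCVA is the primary endpoint for Specific Aim 5, and this paragraph is the protocol's only statement of what REAGIR II can detect on it. A reader who takes it at face value would think the study sensitive only to effects above five lines, and might discount a null result for that reason. The inputs quoted imply sensitivity to a little over two lines. If a larger SD was in fact used, the problem is different: the sentence carrying over the SCUT II assumptions is wrong and the real input is hidden. At an SD of 0.66, for example, power for 0.23 logMAR would be about 23%, not 80%.

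**Working it through.** **Inputs (all from Protocol 9.2)**

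- SD 0.293 and baseline correlation 0.216, so the residual SD is 0.293 × √(1 − 0.216²) = 0.2861, rounded to 0.286.
- Alpha 0.05. The paragraph does not say whether this is one- or two-sided. I take it as two-sided, the reading that reproduces the neighbouring figures.
- 30 per arm with 15% loss: 30 × 0.85 = 25.5 evaluable per arm.

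**Formula.** For a two-sample t-test with n evaluable per arm, power is the probability that a noncentral t variable with 2n − 2 degrees of freedom and noncentrality δ / (SD × √(2/n)) exceeds the two-sided critical value. I solve for δ. The normal approximation is δ ≈ SD × √(2/n) × (z for 1 − α/2 + z for power).

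**Step 1: reproduce the neighbouring figures (SD 0.286).**

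| Statement | Evaluable per arm | Alpha | Power | Stated | Computed |
|---|---|---|---|---|---|
| SCUT II, 93 per arm | 79 | 0.025 | 80% | 0.14 | 0.141 |
| SCUT II, 60 per arm | 51 | 0.025 | 80% | 0.18 | 0.177 |
| REAGIR, 165 per arm | 140 | 0.05 | 90% | 0.11 | 0.111 |
| REAGIR, 165 per arm | 140 | 0.05 | 80% | 0.10 | 0.096 |

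All four agree to rounding.

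**Step 2: REAGIR II by the same method (SD 0.286, alpha 0.05).**

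| Evaluable per arm | 80% power | 90% power |
|---|---|---|
| 25 | 0.231 | 0.268 |
| 25.5 | 0.229 | 0.265 |
| 26 | 0.227 | 0.262 |
| 30 (no loss) | 0.210 | 0.243 |
| **Stated** | **0.53** | **0.61** |

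Normal approximation at 25.5 per arm: 0.286 × √(2/25.5) × (1.960 + 0.842) = 0.224 at 80% power, and 0.286 × √(2/25.5) × (1.960 + 1.282) = 0.260 at 90%. At 25.5 per arm the ratios of stated to computed are 0.53/0.229 = 2.31 and 0.61/0.265 = 2.30. With 25 per arm, power for 0.53 exceeds 99.99%.

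**Step 3: try other readings.**

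- Unadjusted SD 0.293, 25.5 per arm: 0.235 and 0.271.
- Alpha 0.025 two-sided, 25 per arm: 0.256 and 0.293.
- 30 misread as the total for both arms (12 to 15 per arm), even at alpha 0.025: at most 0.382 and 0.437.
- One-sided testing lowers the values.

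None reaches 0.53 and 0.61.

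**Step 4: check using only the protocol's figures.** The detectable difference scales roughly with 1/√n.

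- From SCUT II: 0.18 × √(60/30) = 0.255 at alpha 0.025, and lower at 0.05.
- From REAGIR, with the same alpha and loss: 0.10 × √(165/30) = 0.235 at 80% power, and 0.11 × √(165/30) = 0.258 at 90%.

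**Step 5: what would give the stated pair?** Holding 25.5 per arm, the SD would have to be 0.662 (from the 80% figure) or 0.659 (from the 90% figure). Holding SD 0.286, the evaluable number would have to be 5.7 to 5.8 per arm. Intermediate pairs also fit: SD 0.40 with 10 per arm, or 0.50 with 15. The second figure adds almost nothing, because the 90%-to-80% ratio is 1.157 to 1.160 for any n from 5 to 30 (stated ratio: 0.61/0.53 = 1.15).

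**The case against.** The strongest reply is that the documents prove an inconsistency, not that 0.53 and 0.61 are the wrong numbers. SD 0.286 comes from SCUT patients with vision between 20/60 and 20/400, whereas REAGIR II admits anyone at 20/40 or worse with no limit at the poor end for the study eye. A larger SD could be justified. If the paragraph's own 30 per arm and 15% loss are kept, both figures point to an SD of 0.65–0.67. On that reading only the sentence borrowing the SCUT II assumptions is wrong. This stands as a caution about cause: 2.3 times too large is a statement relative to the inputs the protocol names. It does not remove the contradiction, and an SD near 0.66 remains an inference.

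The second reply is that little depends on the figure. REAGIR II is a feasibility study, the summary of changes links the target of 60 to the added Brazilian site, no decision rule uses 0.53, and a null result can be read from its confidence interval. Under SD 0.286 the error also understates sensitivity and does not overclaim power. All of that is fair and limits the severity, but a published power statement should still follow from its stated basis.

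Third, Protocol 9.4.1 refers to a REAGIR II SAP that was not among the documents reviewed. It may name the SD used. That could settle the cause but would leave the protocol text contradicting itself.

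**Conclusion.** The point holds. On the inputs named in Protocol 9.2 (residual SD 0.286, two-sided alpha 0.05, 30 per arm, about 15% loss, t-test), the detectable difference is 0.227–0.231 logMAR at 80% power and 0.262–0.268 at 90%, against the stated 0.53 and 0.61. Confidence in the inconsistency is high, because the same method returns the SCUT II and REAGIR figures and simple scaling of those figures gives the same answer.

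The cause cannot be told from the documents: a different SD, a different evaluable number and a slip in the formula all remain possible. The replacement figures of about 0.23 and 0.26–0.27 therefore apply only if SD 0.286 was intended. This should be corrected, but it does not threaten the study's design, its test or its alpha, and it gives no reason to doubt the SCUT II or REAGIR calculations.

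**What to change.** State in Protocol 9.2 the SD and the evaluable number per arm actually used for REAGIR II, then correct one side:

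- **If SD 0.286 was intended**, restate the detectable differences as about 0.23 logMAR (2.3 lines) at 80% power and 0.26–0.27 logMAR (2.6–2.7 lines) at 90%. The exact value depends on whether 25.5 evaluable per arm is rounded up or down.
- **If another SD was used**, remove the sentence carrying over the SCUT II assumptions and give that SD with its source.

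Check that the REAGIR II SAP agrees. REAGIR's power needs a second look only if a larger SD is adopted and judged credible for REAGIR's own population.

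The cost is two or three sentences in Protocol 9.2. No participants are added, and alpha, the analysis and the REAGIR SAP are unchanged.
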